## Study Protocol

### Eligibility Screening

**Internet Prescreen.** Individuals interested in participating in the study will be directed via various recruitment strategies to an Internet prescreen using REDCap. This prescreen is a joint prescreen used by several other IRB-approved smoking studies. The prescreen procedure is the first point of contact for participants, and it will allow us to ask critical information about the potential participant's willingness and ability to commit to the frequency of clinic visits as well as the assessment of inclusion criteria. If a participant passes the Internet Prescreen, they will be directed to a scheduling platform called You Can Book Me. Participants will sign up for a time slot for the phone screen.

**Phone Screening.** The phone screen is an opportunity for research assistants to give potential participants more information about the study and to further assess inclusion/exclusion criteria. Research assistants will follow a phone screen script (see attachment) which includes the Columbia-Suicide Severity Rating Scale (C-SSRS; see Measures). If there is evidence of a suicidal risk, the trained research assistants will follow the Suicidality Standard Operating Procedures (see attachments). Participant responses will be stored on REDCap. Participants who are interested and eligible will schedule an additional phone screen with the study nurse, [name], to discuss their medical history. Participants who are not interested, or ineligible will be provided with smoking treatment referrals (see phone screening script).

**Baseline Survey.** The Baseline survey will be administered during CET 1 during the waiting period for the study drug. This will include further demographic measures, medical questions, and baseline smoking measures such as the Smoking Cue Appeal Survey (SCAS) and Overall Anxiety Scale (OASIS). Previously, all of these questions were included in the Internet Prescreen survey. The Internet Prescreen has been shortened to more effectively recruit participants.

**In-Person Physical Exam.** The ICD will be sent to participants via REDCap before the appointment so that they have time to read through the form and give their informed consent by signing the form digitally with a mouse or mouse pad. Upon arrival, if the participant has not signed the ICD, they will first read the ICD on a computer or iPad and provide their signature if they choose to participate. A study coordinator will be available to answer any questions the participant may have about the study and participation. If the individual chooses to sign the informed consent, he or she will proceed with the physical exam. Study personnel trained in advanced health assessment (PI, [name], RN, FNP-C or other qualified study personnel under the supervision of [name]) will conduct a cardiac and respiratory exam to determine if it is safe for them to take the study medication. In addition to a cardiac and respiratory focused history and physical exam, vital signs to include temperature (Temp), pulse (P), respiratory rate (RR), and blood pressure (BP) will be obtained. Participants will be immediately excluded from the study if any abnormal findings are identified within the cardiac or respiratory physical exam. Vital signs outside normal limits will be handled thusly, (a) BP < 90/60 or >140/90, BP will be reassessed in 5 minutes. If BP is still outside limits participants will reschedule their physical exam within 1 week. If upon return BP is < 90/60 or >140/90 participants will be excluded from the study; (b) P < 60 or >100, recheck in 5 minutes. If P is still outside limits, participant will reschedule their research session within 1 week. If upon return P is < 60 or >100 participant will be excluded from the study; (c) RR >20, RR will be reassessed in 5 minutes, if RR is still outside limits, participants will reschedule their physical exam within 1 week. If upon return RR is >20 participant will be excluded from the study; (d) Temp > 100.4, participants will reschedule their research session within 1 week. If upon return Temp is >100.4 participants will be excluded from the study. If the advanced practice nurse deems it is unsafe for the participant to take the study medication, they will be notified, thanked for their time, and dropped from the study. All eligible participants will continue with the rest of the visit which includes introduction to the goals of research study, and an explanation of data collection documents. Research personnel will also discuss the potential side effects of isradipine with potential participants.

## **Randomization**

[name] or [name] will oversee the randomization to either CE+ISR or CE+PBO conditions. Both participants and study personnel will be blind to study condition, and study medication will be labeled by either "A" or "B" by the pharmacy in order to blind the medication administration. A random number generator will be used to assign individuals to either condition. Only [name] or [name] will have the information necessary to break the blind. Prior to data analyses, [name] will check the balance of randomization and control for any factors that are imbalanced.

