## **Intervention Modules**

***Abstinence Challenge.*** Eligible participants will be required to abstain from smoking beginning 24 hours prior to the physical exam that occurs on the day of the first CE session and up until the time of the second session. Abstinence status will be verified by a Vitalograph Breathco Carbon Monoxide monitor ( $\leq 4$  ppm). If a participant is not abstinent at the time of the physical exam and CE session 1, the participant will be asked to re-schedule within 1 week. In order to ensure compliance with alcohol abstinence 24 hours prior to CE session 1 and 24 hours after CE session 1, abstinence status will be verified by an AlcoBreath measurement at the beginning of CE session 1 and the beginning of CE session 2. If a participant is not abstinent at the time of CE session 1, the participant will be asked to re-schedule within 1 week.

***Ecological Momentary Assessment (EMA).*** Eligible participants will be asked to respond to surveys delivered via text message or email up to 15 times per day 24-hours prior to the physical exam and up until the time of Cue Exposure Session 2 (48 hours total). Participants will be asked various questions related to smoking craving, behavior, and cues (see attached Short Smoking Log).

***Cue Exposure (CE).*** The two 60-minute CE sessions will be conducted to expose participants to interoceptive and situational cues for tobacco use and craving (see Cue Exposure Therapy Protocol attachment). In the first session, participants will receive a dose of ISR or PBO and begin the CE session after waiting 75 minutes. The overarching goal of CE is to expose participants to triggers that will produce high cravings, and to repeat exposure to those triggers in a controlled setting in order to allow the craving to come down on its own. Because not all smokers respond equally to the same triggers, clinicians are trained to apply a variety of approaches. These can include exposure to slides, videos (on a traditional flat screen as well as in 360 video headsets) depicting smoking cues (visual exposure), exposure to emotions and imagined situations that most reliably triggered an urge to smoke (emotional/imaginal), and exposure to a participant's own cigarettes (in vivo). The second session will be conducted 24 h after the first in a medication-free state. Clinicians will record craving throughout the CE sessions (see Reported Craving During CE attachment).

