***Isradipine or Placebo.*** All capsules will be identical in appearance to maintain the blind design of the study. Study capsules will be prepared containing: (a) 15 mg immediate release isradipine or (b) pill placebo. Individual doses of study medications, prescribed by [name], will be dispensed to patients by study personnel 75 minutes prior to CE 1 and patients will be asked to remain in the clinic until session time. Because all pill taking is observed, no pill counts are necessary to help ensure adherence to the randomized drug condition. The drug will be prepared at Abrams Royal ([name]). All medications will be stored in a locked refrigerator. Upon completion of recruitment, unused medication will be returned to the pharmacy for proper disposal.

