***Measures of research integrity, safety, and acceptance***

**Vital Signs.** Participants' blood pressure and heart rate will be assessed. This will be collected during the screening visit, CET visit 1 and 2.

**Patient Adherence.** Patient adherence will be assessed by taking attendance at each session.

**Researcher Adherence.** Each session (for those participants who give consent to be videotaped) will be videotaped and 10% will be rated shortly thereafter by independent raters to assess therapist adherence to, and competence with, the experimental protocol. Participants are not required to be videotaped and will indicate on their ICD whether or not they are willing to participate in the recording of sessions. Sessions from CE visit 1 and 2 will be reviewed.

**Concurrent Treatment.** Use of medications other than nicotine patch or other aids to smoking cessation and participation in any concurrent psychotherapeutic treatment will be assessed. This will be collected during the screening visit, CE visit 1 and 2.

**Safety Monitoring and Concerns.** At each visit, participants will be asked about side effects of the study medication and procedures. Adverse Events forms will be utilized to track any symptoms expressed during study visits. Forms will be reviewed each visit by the study PI, and participants who report significant symptoms or adverse reactions will be interviewed separately. This will be collected during the screening visit, CE visit 1 and 2.

**AlcoBreath Screening.** Participants will be asked to breathe into an AlcoBreath tube in order to assess for the presence of alcohol. Although there are no absolute contraindications to co-administration of isradipine with alcohol, both substances are metabolized through the liver. Participants are advised to refrain from alcohol for at least 24 hours prior to administration of isradipine and 24 hours after administration of isradipine. This will be collected during the screening visit, CE visit 1 and 2.

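### Two arm-level letters on medication handed out by blinded staff mean that one disclosed allocation could decode the whole trial; unique dose numbers would confine it to one participant.

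*Combined protocol and SAP*

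**What the plan says.** The Randomization section of the combined protocol and SAP states that "Both participants and study personnel will be blind to study condition" and that "study medication will be labeled by either 'A' or 'B' by the pharmacy in order to blind the medication administration". Only two roles "will have the information necessary to break the blind". Under Intervention Modules (Isradipine or Placebo), "All capsules will be identical in appearance to maintain the blind design of the study", and individual doses "will be dispensed to patients by study personnel 75 minutes prior to CE 1".

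No section describes a participant-specific, kit or dose number, a further code beneath the letters, or a way to break the blind for one participant alone.

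Three other parts of the plan bear on the point:

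- Under Cue Exposure (CE), the clinicians running the sessions write down the craving that participants report. Because smokers differ in their triggers, "clinicians are trained to apply a variety of approaches".
- Under Safety Monitoring and Concerns, "At each visit, participants will be asked about side effects of the study medication and procedures". One role reviews the forms every visit, and the Assessment Schedule places adverse events at CE visit 2, after the dose given at CE visit 1.
- Under Specific Aim 1, the primary test is the interaction of group with trial, using the first and last trials of CE session 2.

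**The concern.** With two conditions and two labels, the letter becomes a shared key. One disclosure, accidental or legitimate, would identify the arm of every participant whose letter is known to staff.

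The letters also allow weak clues to accumulate. Staff explain isradipine's possible side effects to participants (In-Person Physical Exam), so they know what to look for. Side effects, blood pressure and heart rate are then checked at the CE visits. An impression that is unreliable for one participant becomes more reliable when averaged over everyone with the same letter.

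This matters because the outcome is subjective craving, recorded by clinicians who also choose the exposure approach. A clinician who had learned the key could, without intending to, deliver or record sessions differently for participants not yet assessed. The perceived-treatment item is asked of participants only, so it would not detect decoding by staff.

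**Working it through.** **Inputs.** Total sample 102, 51 per arm, f = 0.1, alpha 0.05, 80% power, correlation 0.75 (C3g, Sample size and power considerations). Two labels, two arms (Randomization). Primary contrast: first against last CE 2 trial, by group (Specific Aim 1).

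**The plan's own sample size.** For the group-by-trial interaction with m = 2 measurements, the noncentrality is λ = f² × N × m / (1 − ρ). At N = 102, λ = 0.01 × 102 × 2 / 0.25 = 8.16 on 1 and 100 degrees of freedom, giving power 0.808. At N = 100 the power is 0.7997, just short of 80%. The stated 102 is therefore reproduced. Labelling does not enter this calculation, so the remedy leaves the sample size unchanged.

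**Reach of a disclosure.** Suppose the key becomes known after k participants have completed CE 2. Craving already recorded is unaffected, so at most 102 − k participants are exposed, a share of (102 − k)/102. The values of k are illustrative.

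| k | Exposed with A/B letters | Share | Exposed with unique numbers |
|---|---|---|---|
| 10 | 92 | 90% | at most 1 |
| 25 | 77 | 75% | at most 1 |
| 51 | 51 | 50% | at most 1 |
| 75 | 27 | 26% | at most 1 |

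Under unique numbers, 1/102 is about 1%. If totals were fixed at 51 per arm, learning one participant's arm would change the chance that any other shares it only from 50% to 50/101 = 49.5%.

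**Pooling of clues by letter.** Assume a staff guess about each participant is right with probability p, independently. Neither the values of p nor independence comes from the documents. The probability that a majority of guesses identifies the key correctly is a binomial tail:

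| p | 21 participants | 51 participants |
|---|---|---|
| 0.55 | 0.68 | 0.76 |
| 0.60 | 0.83 | 0.93 |
| 0.65 | 0.92 | 0.99 |
| 0.70 | 0.97 | above 0.99 |

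This shows how grouping strengthens a weak clue; it does not predict what would happen here. Unique numbers remove the grouping but do not prevent a guess about an individual.

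**Effect on the primary contrast.** Let knowledge of the arm add c_first and c_last to the between-arm difference on the first and last CE 2 trials among exposed participants, taken as evenly split between arms. The contrast then shifts by (c_last − c_first) × (102 − k)/102. The shift is zero when the two influences are equal. Only a differential influence biases the test, for example through the choice of cues during the session. The documents support no value for either term, so no bias or error rate is computed.

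**The case against.** The arrangement is coherent as written: capsules look alike, the pharmacy labels them, few people hold the code, and no unblinding of session staff is planned. Harm requires a chain of events: a fixed letter-to-arm key, session clinicians who see the letters, a disclosure or successful pooling, a change in behaviour, and an effect that differs between the two trials. The documents do not confirm the first two links and give no likelihood or size for the rest. This is a short protocol that refers to attachments not supplied, so a participant-level code could exist elsewhere. Nothing says the adverse event forms carry the letter. The role reviewing them may already hold the code, which cannot be judged with names removed. Craving is the blinded participant's own report, and 10% of videotaped sessions are to be rated independently for therapist adherence and competence.

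Much of this stands. No breach is shown, the percentages count participants who could be exposed and do not measure an effect, and an influence equal on both trials cancels. That is why the point is minor.

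None of it limits the reach of a disclosure once it occurs, however. Identical capsules and a small circle of code holders make disclosure less likely, but they do not contain it. Adherence ratings on a tenth of recorded sessions neither prevent decoding nor confine it. Separation of dispensers from session clinicians is not stated, so it cannot be relied on.

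**Conclusion.** The point holds as a minor weakness in a design choice. Under the stated labelling, one disclosed allocation could reveal the arm of every participant whose letter is known, against one participant with unique numbers.

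The conclusion assumes a fixed letter-to-arm key, and the upper bounds further assume that staff know the letters of all remaining participants. Confidence is medium because the documents do not say who sees the letters or whether those who dispense also run sessions. The likelihood and timing of a disclosure, and any resulting bias in the primary result, cannot be sized from the documents.

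**What to change.** Have the pharmacy label each dose with a unique participant or kit number taken from the randomisation list, and remove any arm-level letter visible to dispensing or session staff. The numbers must be ordered at random so that they carry no information about arm. The list linking number to arm should stay with the roles already allowed to break the blind, away from those who dispense or run sessions. If a further code already lies beneath the letters, a sentence in the Randomization section saying so would settle the point.

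The cost is a numbered label list prepared and kept by the pharmacy, and a match of dose to participant at dispensing. No visits, assessments or participants are added.

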## **Intervention Modules**

***Abstinence Challenge.*** Eligible participants will be required to abstain from smoking beginning 24 hours prior to the physical exam that occurs on the day of the first CE session and up until the time of the second session. Abstinence status will be verified by a Vitalograph Breathco Carbon Monoxide monitor ( $\leq 4$  ppm). If a participant is not abstinent at the time of the physical exam and CE session 1, the participant will be asked to re-schedule within 1 week. In order to ensure compliance with alcohol abstinence 24 hours prior to CE session 1 and 24 hours after CE session 1, abstinence status will be verified by an AlcoBreath measurement at the beginning of CE session 1 and the beginning of CE session 2. If a participant is not abstinent at the time of CE session 1, the participant will be asked to re-schedule within 1 week.

***Ecological Momentary Assessment (EMA).*** Eligible participants will be asked to respond to surveys delivered via text message or email up to 15 times per day 24-hours prior to the physical exam and up until the time of Cue Exposure Session 2 (48 hours total). Participants will be asked various questions related to smoking craving, behavior, and cues (see attached Short Smoking Log).

***Cue Exposure (CE).*** The two 60-minute CE sessions will be conducted to expose participants to interoceptive and situational cues for tobacco use and craving (see Cue Exposure Therapy Protocol attachment). In the first session, participants will receive a dose of ISR or PBO and begin the CE session after waiting 75 minutes. The overarching goal of CE is to expose participants to triggers that will produce high cravings, and to repeat exposure to those triggers in a controlled setting in order to allow the craving to come down on its own. Because not all smokers respond equally to the same triggers, clinicians are trained to apply a variety of approaches. These can include exposure to slides, videos (on a traditional flat screen as well as in 360 video headsets) depicting smoking cues (visual exposure), exposure to emotions and imagined situations that most reliably triggered an urge to smoke (emotional/imaginal), and exposure to a participant's own cigarettes (in vivo). The second session will be conducted 24 h after the first in a medication-free state. Clinicians will record craving throughout the CE sessions (see Reported Craving During CE attachment).

***Isradipine or Placebo.*** All capsules will be identical in appearance to maintain the blind design of the study. Study capsules will be prepared containing: (a) 15 mg immediate release isradipine or (b) pill placebo. Individual doses of study medications, prescribed by [name], will be dispensed to patients by study personnel 75 minutes prior to CE 1 and patients will be asked to remain in the clinic until session time. Because all pill taking is observed, no pill counts are necessary to help ensure adherence to the randomized drug condition. The drug will be prepared at Abrams Royal ([name]). All medications will be stored in a locked refrigerator. Upon completion of recruitment, unused medication will be returned to the pharmacy for proper disposal.

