## **SUMMARY OF VISITS**

	Physical Exam	Cue Exposure Day 1	Cue Exposure Day 2
Length:	30 minutes	2.5 hours	1 hour

Purpose:	
 
- Ecological Momentary Assessment 24-hours prior to Day 1 visit (text)
 
-Determine your eligibility by ensuring that it is safe for you to take isradipine.
 
- Receive \$10 cash payment.
 
	
 
-Take isradipine or placebo, wait 75 min, do 60 min of cue exposure.
 
- Receive \$30 for Day 1 and \$2 per EMA response (up to \$30), for a total of up to \$60 for Day 1.
 
	
 
- Ecological Momentary Assessment 24-hours prior to Day 2 visit (text)
 
- Do 60 min of cue exposure without taking isradipine or placebo (no medication).
 
- Receive \$50 for Day 2 and \$2 per EMA response (up to \$30), for a total of up to \$80 for Day 2.
 

-----------------	---	--	---

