***Assessment Schedule***

Participants will receive thorough assessments prior to and over the course of this study, summarized in the table below.

Measure (number of items)	Online/phone Screen	Daily monitoring until quit attempt	Physical Exam	CE visit 1	CE visit 2	
Initial eligibility screen	X					
Demographics	X					
Columbia Suicide Severity Rating Scale - CSSRS	X					
Overall Anxiety Scale OASIS (5)	X					
Fagerström Test for Nicotine Dependence - FTND (6)	X					
Medical history	X					
Carbon Monoxide (2)			X	X	X	
Minnesota Withdrawal Scale - MWS (15)				X	X	
Smoking Cue Appeal Survey -SCAS (8)	X			X	X	
Pittsburgh Sleep Quality Index - PSQI				X		
Sleep Diary				X	X	
Therapist Adherence				X	X	
Patient Adherence		X		X	X	
Adverse Events			X	X	X	
Vital Signs			X	X	X	
AlcoBreath			X	X	X	
Perceived Treatment					X	
Smoking log surveys		X				

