## Data Analyses

### Specific Aim 1: Effect on Long Term Craving

To examine effects on the target of engagement, we will test the hypothesis that CE+ISR, compared to CE+PBO, will have a greater reduction in reduce subjective craving to smoking cues in a subsequent medication-free cue exposure conducted 24-hours later (CE 2).

Analytic approach: A mixed factorial ANOVA will be used to test whether reduction in craving over the course of CE session 2 significantly differ across groups (CE+ISR vs. CE+PBO). More specifically, a 2X2 mixed (within-between) factorial ANOVA will be conducted with Group (2 levels: CE+ISR vs. CE+PBO) as the between-subject variable and Trials (2 levels: the first and last trials during the CE session 2) as the within-subject variable to examine the Group X Trial interaction effects on craving. A separate analysis (ANCOVA) for the same model will be conducted, controlling for sex and baseline nicotine dependence. In addition, potential moderating roles of sex and baseline smoking severity on the effect of CE+ISR (vs. CE+PBO) on craving at the first trial during the CE session 2 will be explored by using two-way ANOVA to test the Group X Moderator interactions or linear regression models with Group X Moderator interaction terms.

**Specific Aim 2: Feasibility and Acceptability of Implementation:** Descriptive statistics will be calculated for the questionnaire to assess overall clinic staff views of feasibility, acceptability, and ease of implementation. A qualitative descriptive approach will be used to analyze semi-structured interview transcripts using content analysis to systematically code and categorize for trends and patterns in the textual data to remain as close to the staff's experiences as possible. We have successfully used similar approaches in prior studies.

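### The plan collects craving ratings before dosing by EMA but does not use them as a covariate, which forgoes precision mainly for craving at the first CE 2 trial

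*Combined protocol and SAP*

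**What the plan says.** The protocol's Intervention Modules section sends EMA surveys "up to 15 times per day 24-hours prior to the physical exam and up until the time of Cue Exposure Session 2" ("48 hours total"). On content it says: "Participants will be asked various questions related to smoking craving, behavior, and cues". The abstinence paragraph in the same section places the start of abstinence "24 hours prior to the physical exam that occurs on the day of the first CE session", so the exam and dosing share a day and the first 24 hours of EMA precede the capsule. The Summary of Visits pays $2 "per EMA response (up to" $30) for each of two days. In the Assessment Schedule, "Smoking log surveys" appear only under daily monitoring.

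Under Specific Aim 1 the main test is a 2x2 mixed ANOVA with "Trials (2 levels: the first and last trials during the CE session 2) as the within-subject variable". The adjusted analysis reads: "A separate analysis (ANCOVA) for the same model will be conducted, controlling for sex and baseline nicotine dependence". Craving at the first CE 2 trial is also modelled, but only to explore moderation by sex and baseline smoking severity. The Measures section gives the FTND a covariate role and the sleep measures a possible one. It gives EMA none. The Randomization section allows control for factors found to be imbalanced and does not name EMA.

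**The concern.** In the text supplied, the pre-dose EMA surveys are the only measure described as asking about craving before the capsule. Craving during CE 1 cannot serve as a baseline, because that session starts 75 minutes after dosing. A covariate measured before dosing cannot be affected by treatment, so adjusting for it adds no bias in a randomized comparison and removes variance to the extent that it predicts the outcome. What is at stake is precision in the models of CE 2 craving, at no further burden to participants. If the covariate is not named in advance, a later EMA adjustment would be post hoc, or would enter only through the data-driven imbalance check.

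**Working it through.** **Inputs from the documents.** N = 102 (51 per arm), f = 0.1, alpha 0.05, 80% power and a correlation of 0.75 between first and last trial (section C3g). EMA runs at up to 15 surveys per day for 48 hours. The payment cap agrees: 30/2 = 15 paid responses per day, 30 in all, about 15 of them before dosing.

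**Inputs assumed.** The documents do not give the correlation of the pre-dose EMA mean with CE 2 craving. I vary it from 0.3 to 0.7. In a model that already holds sex and nicotine dependence, read it as the correlation left after those terms. Dropout is not applied.

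**1. The plan's sample size.** The noncentrality is f² × N × 2/(1 − rho) = 0.01 × 102 × 2/0.25 = 8.16, with 1 and 100 df. Power is 0.808. At N = 100 it is 0.7997, so 102 is the smallest even N that reaches 80%. The stated figure reproduces.

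**2. Craving level at the first CE 2 trial.** Adjustment multiplies the residual variance by 1 − r². Two-sided t test, 51 per arm:

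| r | 1 − r² | Variance removed | Detectable difference, 80% power | Power if the true difference is 0.4 SD (assumed) |
|---|---|---|---|---|
| 0 | 1.00 | 0% | 0.56 SD | 52% |
| 0.3 | 0.91 | 9% | 0.53 SD | 55% |
| 0.5 | 0.75 | 25% | 0.49 SD | 64% |
| 0.7 | 0.51 | 51% | 0.40 SD | 80% |

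These figures are for a simple difference between arms. The plan's first-trial models test Group by Moderator terms. The same variance factor applies there, but the detectable effect is larger. With a two-level moderator split evenly the standard error doubles, giving about 2 × 0.56 = 1.12 SD unadjusted and 2 × 0.40 = 0.80 SD at r = 0.7.

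**3. The planned Group by Trial test.** With two trials this is a comparison of change scores. A between-person covariate entered as a main effect only cancels from the change. Entered with its interaction with Trial, it helps through its correlation with change: r_change = (r_last − r_first)/√(2 × (1 − 0.75)), where the divisor is 0.707. The noncentrality becomes 8.16/(1 − r_change²).

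| r_first / r_last | r_change | Variance factor | Power at N = 102 |
|---|---|---|---|
| 0.5 / 0.5 (or any equal pair) | 0 | 1.00 | 0.808 |
| 0.5 / 0.4 | −0.141 | 0.98 | 0.815 |
| 0.5 / 0.3 | −0.283 | 0.92 | 0.839 |
| 0.6 / 0.3 | −0.424 | 0.82 | 0.878 |

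**4. EMA after CE 1 as an outcome.** Take 8 to 15 answered surveys, an ICC of 0.3 to 0.7 and a difference of 0.3 single-rating SD (all assumed). The variance of the mean is ICC + (1 − ICC)/m. It runs from 0.3 + 0.7/15 = 0.347 to 0.7 + 0.3/8 = 0.7375. Power from averaging alone is 72% and 42% at these two ends, against 32% for one rating. This treats surveys within a day as independent given the person and assumes the same effect on EMA craving as on in-session craving. The documents support neither assumption.

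**The case against.** The strongest objection is relevance. The Aim 1 hypothesis is tested by Group by Trial, where the covariate may do nothing. The larger gains concern first-trial level, which the plan uses only in exploratory moderator models. This stands, and it limits the size of the point. It does not remove it, because those models are in the plan and interaction tests have little precision to spare.

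A reader might infer that the between-session EMA data are a more precise version of the Aim 1 outcome. The documents do not support that. Aim 1 concerns craving to cues in a medication-free session, whereas EMA asks about craving outside the sessions. Surveys soon after CE 1 are not shown to be medication-free, so a contrast between arms could include acute drug effect. Adding adjustment for the pre-dose mean (assumed person-level correlation between days 0.6 to 0.8) raises the power in step 4 to 57% to 94%. Setting that against 32% for one unadjusted rating is not like for like.

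Three further limits stand:

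- The Short Smoking Log and the CE craving form are attachments not supplied, so the EMA item and scale cannot be compared with the in-session rating.
- Pre-dose EMA covers roughly the first 24 hours of abstinence, while CE 2 falls near hour 48. It is a related baseline, not an identical one.
- EMA may also serve to monitor adherence, since the Assessment Schedule marks patient adherence under daily monitoring. That would not prevent its use as a covariate.

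**Conclusion.** The point holds as a missed use of baseline data, not as an error in the planned test. Under assumed correlations of 0.3 to 0.7, the pre-dose EMA mean would cut the variance of first-trial craving by 9% to 51%. That is equivalent to needing 102 × 0.91 = 93 down to 102 × 0.51 = 52 participants for the same precision. The Group by Trial test gains nothing if EMA craving predicts both trials equally. It gains about 0.01 to 0.07 in power if the two correlations differ by 0.1 to 0.3. A reader should not conclude that the trial is underpowered on its own assumptions or that N = 102 is wrong, because that figure reproduces. The size of any gain rests on correlations and response rates that the documents do not report.

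**What to change.** Under Specific Aim 1, before unblinding:

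- Define the covariate as each participant's mean EMA craving over the 24 hours before the CE 1 visit that was actually completed. This settles which window applies when a visit is rescheduled.
- Add it to the models of first-trial CE 2 craving, and to the ANCOVA together with its interaction with Trial.
- State a simple imputation for participants with no pre-dose response, made without regard to arm.
- Optionally, name one secondary linear mixed model of EMA craving after CE 1 by arm, adjusted for the pre-dose mean, with a random participant intercept. Describe it as craving outside the sessions, and state the survey window or a time term and the handling of missed surveys. If this is not wanted, say that post-CE 1 EMA is descriptive or for adherence.

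The cost is plan wording and programming. No new data, visits or participants are needed.
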